Initiation of mechanical ventilation for critically ill patients is frequently a time-sensitive procedure. Despite the availability of a formal informed consent document for tracheal intubation and initiation of mechanical ventilation, time allows for discussion of risks and benefits of these clinical procedures in less than 10% of cases during clinical care in the study ICU. Titration of FiO_2 to target SpO_2 in PILOT begins within 15 minutes of the initiation of mechanical ventilation with a goal of intervening during the period with the highest prevalence of excess FiO_2 , hyperoxemia, and hyperoxia. Moreover, in this cluster-randomized trial, the entire ICU is assigned to a single SpO_2 target delivered by the unit's respiratory therapists through a unit-wide oxygen titration protocol. Obtaining informed consent from every patient receiving invasive mechanical ventilation in the study ED and ICU prior to the initiation of invasive mechanical ventilation would be impracticable and would potentially delay delivery of a time-sensitive intervention.

Because the study presents minimal incremental risk, the study does not adversely affect the welfare or privacy rights of the participants, and obtaining informed consent prior to enrollment is impracticable, the study is being conducted with a waiver of informed consent.

27. Plan for Communication of Protocol Changes

Any changes to the trial protocol (e.g., changes to eligibility criteria, outcomes, analyses) will require a new version of the full trial protocol which will be tracked with the date of the update and the version number of the trial protocol. A list summarizing the changes that are made with each protocol revision will be included at the end of each protocol. The updated protocol will be sent to the Vanderbilt IRB for approval prior to implementation of the protocol change. At the time of publication, the original trial protocol and the final trial protocol, including the summary of changes made with each protocol change, will be included in the supplementary material for publication.

28. Patient Privacy and Data Storage

All patients are assigned a unique study ID number for tracking. Data collected from the medical record is entered into the secure online database REDCap. All data is maintained in the secure online database REDCap until the time of study publication. At the time of publication, a de-identified database will be generated.

29. Data Sharing Plan

Upon reasonable request, a completely de-identified data set may be provided by the authors. Request to share data from the PILOT trial should be sent to the principal investigator, [name], at [contact]. The dataset will be provided to researchers whose proposed use of the data has been approved by the PILOT steering committee and an Institutional Review Board and is accompanied by an executed Data Use Agreement.

SUPPLEMENTAL TABLES**Table S1. Modified Non-respiratory SOFA Score.**

	0	1	2	3	4
Coagulation Platelets (x10³/mm³)	> 150	101-150	51-100	21-50	≤ 20
Liver Bilirubin (mg/dL)	< 1.2	1.2-1.9	2.0-5.9	6.0-11.9	≥ 12
Cardiovascular Blood pressure	Mean arterial pressure ≥ 70 mmHg and no receipt of dopamine, dobutamine, epinephrine, or norepinephrine	Mean arterial pressure < 70 mmHg and no receipt of dopamine, dobutamine, epinephrine, or norepinephrine	On dopamine ≤ 5 mcg/kg/min or any dobutamine	On dopamine > 5 mcg/kg/min, epinephrine ≤ 0.1 mcg/kg/min, or norepinephrine ≤ 0.1 mcg/kg/min	On dopamine > 15 mcg/kg/min, epinephrine > 0.1 mcg/kg/min, or norepinephrine > 0.1 mcg/kg/min
Brain Glasgow coma score	15	13-14	10-12	6-9	< 6
Kidney Renal function	Creatinine <1.2 mg/dL	Creatinine 1.2-1.9 mg/dL	Creatinine 2.0-3.4 mg/dL	Creatinine 3.5-4.9 mg/dL	Creatinine > 5 mg/dL

The Sequential Organ Failure Assessment (SOFA) score (Vincent et al Critical Care Medicine 1998) is composed of scores from six organ systems, graded from 0 to 4 according to the degree of dysfunction or failure. Scores range from 0 (no evidence of organ dysfunction or failure) to 24 (evidence of severe dysfunction failure in each of the six organ systems). The modified non-respiratory SOFA score is composed of scores from five of the six organ systems included in the complete SOFA score (excluding the respiratory system), graded on the same scale as the complete SOFA score. Scores range from 0 (no evidence of organ dysfunction or failure) to 20 (evidence of severe organ dysfunction or failure in each of the five organ systems assessed).

SUPPLEMENTAL REFERENCES

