5.0 Inclusion and Exclusion Criteria

5.1 Inclusion Criteria:

1. Age \geq 18 years
2. Receiving mechanical ventilation through an endotracheal tube or tracheostomy
3. Admitted to the study ICU or admission to the study ICU from the emergency department is planned

5.2 Exclusion Criteria:

1. Known pregnancy or beta hCG level greater than the laboratory upper limit of normal in a patient capable of becoming pregnant
2. Known to be a prisoner

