7.4 Outcome Measures

Primary Outcome:

The primary outcome is ventilator-free days (VFDs) to study day 28. VFDs will be defined as the number of calendar days alive and free of invasive mechanical ventilation from the final receipt of invasive mechanical ventilation through 28 days after enrollment. For the assessment of VFDs, the day of enrollment (defined as the day on which the patient first receives invasive mechanical ventilation in a participating study location), will be considered to be day 0. Outcome ascertainment will cease at the time of hospital discharge or 28 days after enrollment, whichever occurs first. Receipt of invasive mechanical ventilation will be considered to end when patients undergo the final tracheal extubation or disconnection of the ventilator from the endotracheal tube or tracheostomy tube between enrollment and 28 days after enrollment. Patients who continue to receive invasive mechanical ventilation at day 28 will receive zero VFDs. Patient who die prior to day 28 will receive zero VFDs. Patients who are discharged from the hospital prior to day 28 and are receiving invasive mechanical ventilation at the time of discharge will receive zero VFDs. Patients who are removed from invasive mechanical ventilation and are discharged from the hospital without invasive mechanical ventilation prior to 28 days will be assumed to remain free of invasive mechanical ventilation between hospital discharge and day 28. For patients who are removed from invasive mechanical ventilation, return to invasive mechanical ventilation, and are subsequently removed again from invasive mechanical ventilation prior to day 28, VFDs will be counted from the final receipt of invasive mechanical ventilation prior to day 28. We chose VFDs as the primary outcome for the PILOT trial as choice of SpO_2 target may simultaneously affect both mortality and duration of invasive mechanical ventilation.

Secondary Outcome:

The sole pre-specified secondary outcome is 28-day in-hospital mortality, defined as death from any cause between enrollment and the first of hospital discharge or 28 days after enrollment.

Exploratory Clinical Outcomes:

1. ICU mortality
2. Vasopressor-free days
3. Renal replacement therapy-free days
4. ICU-free days
5. Hospital-free days

Exploratory Organ Function Outcomes: (All exploratory organ function outcomes will employ only laboratory values and imaging obtained as a part of routine clinical care)

1. Daily non-respiratory SOFA score

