The sole pre-specified secondary outcome is 28-day in-hospital mortality, defined as death from any cause between enrollment and the first of hospital discharge or 28 days after enrollment.

Exploratory Clinical Outcomes

1. ICU mortality – death in the ICU between enrollment and the first of 28 days after enrollment or hospital discharge
2. Free-day outcomes – defined as whole calendar days from last receipt of therapy until 28 days (supplemental file 1, section 19)
 - a. Vasopressor-free days
 - b. Renal replacement therapy-free days
 - c. ICU-free days
 - d. Hospital-free days

Exploratory Organ Function Outcomes

1. Daily non-respiratory SOFA score (Table S1) [47]
2. Plasma creatinine concentration (mg/dL)

3. Plasma lactate concentration (mmol/L)
4. Presence of acute respiratory distress syndrome by Berlin criteria [48]
5. Stage II or greater AKI by Kidney Disease: Improving Global Outcomes (KDIGO) creatinine criteria [49]

Exploratory Safety Outcomes

1. Atrial arrhythmia
2. Ventricular arrhythmia
3. Cardiac arrest with return of spontaneous circulation
4. Pneumothorax or pneumomediastinum
5. Ischemic stroke
6. Myocardial infarction [50]

Additional Long-term Patient-Important Outcomes

The independently-funded Cognitive Outcomes in the Pragmatic Investigation of Optimal Oxygen Targets (CO-PILOT) study (R21AG063126) will assess cognitive, physical, and psychological outcomes at 12 months after enrollment in the PILOT trial. The protocol and statistical analysis plan for the CO-PILOT study will be published separately.

Statistical Analysis and Reporting

Sample Size Estimation and Power Calculation

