patient registration, billing and laboratory clinical information systems into an Enterprise Data Warehouse. We have previously validated the quality of the automated method of data collection against the reference standard of two-physician manual chart review⁴¹ and have employed this approach for the conduct of prior pragmatic trials.^{42 43} Data are stored, curated and secured in REDCap.⁴⁴

Outcomes

Primary outcome

The primary outcome is VFDs to study day 28. VFDs will be defined as the number of whole calendar days alive and free of invasive mechanical ventilation beginning at midnight on the day of the final receipt of invasive mechanical ventilation through day 28 after enrolment.^{45 46} Outcome ascertainment will cease at the time of hospital discharge or 28 days after enrolment, whichever occurs first. Receipt of invasive mechanical ventilation will be considered to end when patients undergo the final tracheal extubation or disconnection of the ventilator from the endotracheal tube or tracheostomy tube between enrolment and 28 days after enrolment. Patients whose final receipt of invasive mechanical ventilation occurs on the day of enrolment will receive 27 VFDs. Patients who continue to receive invasive mechanical ventilation 28 days after enrolment will receive 0 VFDs. Patients who die prior to day 28 will receive 0 VFDs. Patients who are discharged from the hospital prior to day 28 and are receiving invasive mechanical ventilation at the time of discharge will receive 0 VFDs. Patients who are removed from invasive mechanical ventilation and are discharged from the hospital without invasive mechanical ventilation prior to 28 days will be assumed to remain free of invasive mechanical ventilation between hospital discharge and day 28. For patients who are removed from invasive mechanical ventilation, return to invasive mechanical ventilation, and are subsequently removed again from invasive mechanical ventilation prior to day 28, VFDs will be counted from the final receipt of invasive mechanical ventilation prior to day 28.

Secondary outcome

The sole prespecified secondary outcome is 28-day in-hospital mortality, defined as death from any cause between enrolment and the first of hospital discharge or 28 days after enrollment.

Exploratory clinical outcomes

1. ICU mortality—death in the ICU between enrolment and the first of 28 days after enrolment or hospital discharge

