Each of the outcomes related to the number of days alive and free of a specific supportive therapy (e.g., vasopressor-free days, renal replacement therapy-free days, ICU-free days, and hospital-free days) will be defined using the same approach as the primary outcome of ventilator-free days.

Days alive and free of the supportive therapy will be defined as the number of calendar days alive and free of the supportive therapy from the final receipt of the supportive therapy through 28 days after enrollment [67,68]. The day of enrollment will be considered to be day 0. Outcome ascertainment will cease at the time of hospital discharge or 28 days after enrollment, whichever occurs first.

Receipt of the supportive therapy will be considered to end at the time of the patient's final receipt of the supportive therapy between enrollment and 28 days after enrollment. Patients who continue to receive the supportive therapy at day 28 will receive a value of zero. Patients who die prior to day 28 will receive a value of zero. Patients who are discharged from the hospital prior to day 28 and are receiving the supportive therapy at the time of discharge will receive a value of zero. Patients who are removed from the supportive therapy and are discharged from the hospital without the supportive therapy prior to 28 days will be assumed to remain free of the supportive therapy between hospital discharge and day 28. For patients who are removed from the supportive therapy, return to receiving the supportive therapy, and are subsequently removed again from the supportive therapy prior to day 28, days alive and free of the supportive therapy will be counted from the final receipt of the supportive therapy prior to day 28.

20. Measures of Separation between Groups and Processes of Care

Measures of Separation between Groups

1. SpO₂ during invasive mechanical ventilation
2. SaO₂ during invasive mechanical ventilation
3. FiO₂ during invasive mechanical ventilation
4. PaO₂ during invasive mechanical ventilation
5. Episodes of hypoxemia, including:
 - a. SpO₂ < 85% for \geq 5 minutes
 - b. SpO₂ < 80% for \geq 5 minutes
 - c. SpO₂ < 70% for \geq 2 minutes
6. Episodes of hyperoxemia, including:
 - a. SpO₂ > 98% for \geq 5 minutes
 - b. SpO₂ > 98% for \geq 30 minutes
7. Proportion of patients with a value for PaO₂ < 55 mm Hg
8. Proportion of patients with a value for PaO₂ > 120 mm Hg

Measures of Processes of Care

1. Tidal volume
2. Positive end-expiratory pressure

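### RRT-free days and Stage II or greater AKI make no allowance for chronic dialysis that predates the illness, so both exploratory outcomes include values that say nothing about the SpO₂ target

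*Combined protocol and SAP*

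**What the plan says.** Section 19 of the online supplement covers vasopressor-, RRT-, ICU- and hospital-free days, which "will be defined using the same approach as the primary outcome of ventilator-free days". Three rules lead to zero:

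- death: "Patients who die prior to day 28 will receive a value of zero";
- therapy at the end of follow-up: "Patients who continue to receive the supportive therapy at day 28 will receive a value of zero";
- therapy at discharge: those "discharged from the hospital prior to day 28 and are receiving the supportive therapy at the time of discharge will receive a value of zero".

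None of them separates therapy started during the index illness from therapy the patient was already receiving. The primary outcome has the same discharge rule for invasive ventilation (current protocol, section 7.4: "discharged from the hospital prior to day 28 and are receiving invasive mechanical ventilation at the time of discharge will receive zero VFDs"; SAP, Primary outcome: "receiving invasive mechanical ventilation at the time of discharge will receive 0 VFDs").

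Among the exploratory organ function outcomes, the SAP lists "Stage II or greater AKI by Kidney Disease" (the KDIGO creatinine criteria). It states no exclusion for patients already on dialysis.

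Section 5.1 of the current protocol requires only adult age, "Receiving mechanical ventilation through an endotracheal tube or tracheostomy", and actual or planned admission to the study ICU. The exclusions in section 5.2 are pregnancy and being a prisoner, and section 6.2 says that other clinical factors do not limit entry. Section 11.0 of the protocol compares exploratory outcomes using models with group and time as the only covariates.

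**The concern.** A free-day outcome is meant to record how soon a patient came off a therapy and stayed alive. A patient who arrives on chronic dialysis and leaves on it has returned to baseline, yet scores the same as a patient who died. That score was settled before enrolment, whatever the assigned SpO₂ target did.

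AKI has a related problem. In a patient already on dialysis, creatinine reflects the dialysis and not new kidney injury, so a Stage II call is hard to interpret either way.

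What is at stake is the interpretability and precision of two exploratory outcomes. No planned analysis separates these patients: the baseline-adjusted analysis (supplement section 23) repeats only the VFD analysis, and chronic RRT is not among its covariates.

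**Working it through.** **The plan's own figure.** The power section gives 2,250 patients, SD 11.4, a 2.0-day difference, two-sided alpha 0.05 and 92% power. With 2,250 / 3 = 750 per group, the SE is 11.4 × √(2/750) = 0.589 days. Then 2.0 / 0.589 = 3.397, and power is Φ(3.397 − 1.960) = 92.5%. The stated figure reproduces and is not in dispute. It concerns VFDs; the documents give no SD, expected mean or target difference for RRT-free days.

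**Applying the scoring rules.**

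- Chronic dialysis, extubated on day 2, discharged before day 28 and still on dialysis: 0 RRT-free days.
- Chronic dialysis, alive and still on dialysis at day 28: 0.
- Death before day 28: 0.

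The three are indistinguishable on this outcome.

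**Dilution of RRT-free days.** Let c be the share of patients on chronic dialysis, scored zero in every arm. Each arm's mean is (1 − c) times the mean in its other patients, so the between-arm difference is multiplied by (1 − c). The documents give no value for c. Assuming 5–10%:

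- c = 5%: 750 × 0.05 = 37.5 patients per arm; the difference is multiplied by 0.95.
- c = 10%: 750 × 0.10 = 75 per arm; the difference is multiplied by 0.90.

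Some of these patients would score zero through death anyway. If the background in-hospital mortality of 25–35% (protocol section 2.0) applied to them, the survivors set to zero by the therapy rules would number 37.5 × 0.65 = 24 to 75 × 0.75 = 56 per arm.

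**Precision on an ordinal outcome.** The planned model is proportional odds, so the mean calculation is only a guide. A rank-test simulation on an assumed VFD-like distribution (median 21, quartiles 0 and 25, SD 11.3; 1,500 simulated trials per setting) compared keeping the fixed zeros with leaving those patients out. Power was 93.4% against 94.1% at c = 5%, and 92.1% against 94.0% at c = 10%. This illustrates direction and rough size; it is not a power figure for RRT-free days.

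**AKI.** No figure can be computed, because the documents give neither an AKI rate nor a share on dialysis.

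**Same rule, primary outcome.** Assume 1–3% of patients were on long-term invasive ventilation before admission (2,250 × 0.01 to 0.03, about 23 to 68 patients). The planned difference becomes 2.0 × 0.99 = 1.98 to 2.0 × 0.97 = 1.94 days. With the SD held at 11.4, power is 92.0% to 90.9%, against 92.5%.

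**The case against.** The strongest reply is that little depends on this. Both outcomes are exploratory, and the supplement (section 24) puts the emphasis there on estimates with confidence intervals. Chronic dialysis is fixed before enrolment and scored identically in every arm, so the rule cannot favour a target. Every prevalence above is assumed. All of this stands, and it keeps the point small. What remains is that the values are uninformative and easily set aside.

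A second reply is that receiving a therapy at discharge is undefined for an intermittent therapy. A patient last dialysed on day 9 and discharged on day 10 might be read as off RRT and assumed to stay off, giving about 28 − 9 = 19 free days. That reading also misdescribes a chronic-dialysis patient, and it leaves the score to the analyst. It therefore supports the change.

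Three stronger readings may tempt a reader, and the documents do not support them.

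- *A chance imbalance in dialysis patients would pass for a treatment effect.* At an assumed 7.5%, the SE of a between-arm difference in prevalence is √(2 × 0.075 × 0.925 / 750) = 1.36 points, and 1.96 SE is 2.7 points. If other patients average 20 days (assumed), that moves the mean by 0.027 × 20 = 0.5 days. With an assumed SD of 10–13 days, the 95% half-width is 1.96 × SD × √(2/750) = 1.0–1.3 days. This is ordinary sampling variation that the interval already covers. Allocation is by two-month block, so prevalence that varied by period could widen the imbalance, but the documents give no such figure.
- *The primary outcome is materially compromised.* The figures above show a loss of 0.02–0.06 days. Effect modification by duration of ventilation before enrolment is already planned. Its top category in the protocol, over 360 minutes, does not isolate home ventilation, but it is a related check. Home non-invasive ventilation is not counted at all.
- *An earlier safeguard was removed.* Protocol version 1.0 lists end-stage renal disease only as an extra covariate in the effect-modifier model. Its adjusted VFD model did not include it, and neither model concerned RRT-free days or AKI.

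**Conclusion.** The point holds as a minor one. As written, the plan puts values that carry no information about the SpO₂ target into RRT-free days, and it assesses creatinine-based AKI in patients already on chronic dialysis. The consequence is dilution and noise in two exploratory outcomes, not bias towards any arm. At an assumed 5–10% on chronic dialysis, a true difference in mean RRT-free days shrinks by about 5–10%; a lower prevalence would shrink it proportionately less. The size of the AKI problem cannot be estimated from the documents. The effect on VFDs is very small and gives no reason to change the main analysis.

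**What to change.** In supplement section 19 and in the SAP's exploratory outcomes, specify that RRT-free days and Stage II or greater AKI are analysed among patients not receiving chronic RRT before the index hospitalisation. Report the number excluded in each arm. Because the restriction uses pre-enrolment status, it does not select on anything the intervention could have changed.

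The cost is a few lines of SAP wording, a somewhat smaller denominator for two outcomes, and one check. Supplement section 18 lists baseline comorbidities as collected manually but does not itemise them, so the trial team must confirm that the field identifies chronic RRT.

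Leave the main VFD analysis unchanged. A VFD sensitivity analysis that excludes patients on long-term invasive ventilation before admission is optional. It would need the same check on the baseline data and is unlikely to move the result.

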The protocol determines the SpO₂ target from enrollment until the first of: (1) discontinuation of invasive mechanical ventilation, (2) transfer out of a participating study location, (3) completion of an SpO₂ target modification sheet by treating clinicians, or (4) end of the two-month study period. The protocol does not determine the SpO₂ target during time-periods in which the patient is not physically located in a study location (e.g., during transport) or when FiO₂ is being administered for purposes other than achieving a target SpO₂ (e.g., when an FiO₂ of 1.0 is being administered for a procedure).

At any time, if a treating clinician or a patient, family member, or surrogate feels that an SpO₂ target other than that assigned by the study would be best for the optimal treatment of the patient for any reason, the SpO₂ target for that patient is modified. To modify the target, the respiratory therapist and supervising physician complete a one-

page SpO₂ target modification sheet documenting the new SpO₂ target and the rationale for modifying the target. Examples of conditions for which the assigned SpO₂ target may be modified that were specified in the initial trial protocol included: pneumothorax; pneumomediastinum; carbon monoxide poisoning; decompression sickness; bleomycin toxicity; paraquat toxicity. Examples of conditions for which the assigned SpO₂ target may be modified that were not explicitly specified in the initial trial protocol include: severe chronic obstructive pulmonary disease; severe acute respiratory distress syndrome; severe anemia; status post lung transplantation; and receipt of extracorporeal membrane oxygenation support. Trial protocol directs only the titration of FiO₂ to the assigned SpO₂ target. Other aspects of invasive mechanical ventilation, such as tidal volume [4], positive end-expiratory pressure [39,40], and use of rescue therapies for hypoxemia, are determined by institutional protocols and treating clinicians (see sections 9-17 of supplemental file 1).

Blinding

Similar to prior studies of SpO₂ targets among critically ill adults [22,24,26], patients and clinicians will not be blinded to study group assignment.

Data Collection

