Patients who discontinue invasive mechanical ventilation and return to invasive mechanical ventilation in a study location during the same two-month study period continue to be managed using the same assigned SpO₂ target. Similarly, patients who are transferred out from a study location and return to receiving invasive mechanical ventilation in a study location during the same two-month study period continue to be managed using the same assigned SpO₂ target. Patients who remain on invasive mechanical ventilation in a study location through the end of a two-month study period receive the SpO₂ target assigned by the study until midnight on the night that the two-month study period ends, after which time treating clinicians determine the SpO₂ target with which the patient is managed. Similarly, for patients who are enrolled during one two-month study period, discontinue invasive mechanical ventilation or transferred out of the study location, and return to receiving invasive mechanical ventilation during a subsequent two-month study period, treating clinicians determine the SpO₂ target with which the patient is managed during the subsequent episode of invasive mechanical ventilation.

9. Liberation from Mechanical Ventilation

Each day of mechanical ventilation, all patients in the study ICU are assessed for safety of a spontaneous awakening trial (SAT) and spontaneous breathing trial (SBT) [23] using the SAT and SBT safety criteria from the Awakening and Breathing Controlled trial [24]. To prevent patients in the higher SpO₂ target group from experiencing delays in qualifying for an SBT based on receipt of higher FiO₂ to achieve the higher SpO₂ target, patients in all groups are allowed to qualify for an SAT and SBT regardless of their current FiO₂ or PEEP settings, as long as the other SAT and SBT Safety Screen criteria are met and treating clinicians feel performance of an SAT and SBT is safe. Definitions of SAT and SBT failure and the ventilator settings and duration of the SBT are the same as those used in the ABC trial and during clinical care in the study ICU. For patients who have passed an SBT, the decision to discontinue invasive mechanical ventilation is made by the treating clinicians.

10. Protocol for Ventilator Management in the Study ICU

Predicted Body Weight (PBW) Calculation:

Males: PBW (kg) = (height in inches – 60)*2.3+50

Females: PBW (kg) = (height in inches – 60)*2.3+45.5

Mode: Assist Control

Tidal volume: 6 ml/kg PBW

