3. Peak airway pressure
4. Receipt of mandatory ventilator mode
5. Number of arterial blood gasses
6. Hemoglobin
7. Red cell transfusion

21. Assessment of Compliance with the Assigned SpO₂ Target

All SpO₂ values measured during invasive mechanical ventilation are assessed for compliance with the assigned SpO₂ target. An SpO₂ value is considered compliant with the trial protocol if any of the following conditions are met:

1. Measured SpO₂ is within the target range
2. Measured SpO₂ is above the target range and the FiO₂ is 21%
3. Measured SpO₂ is below the target range and the FiO₂ is 100%
4. Measured SpO₂ occurs after treating clinicians have completed an SpO₂ target modification sheet

22. Interim Analysis

On March 23, 2020, the DSMB conducted a single, planned interim analysis for efficacy and safety at the anticipated halfway point of the trial. The interim analysis included data from patients enrolled during the first 18 months of the trial. According to the criteria specified in the trial protocol, the stopping boundary for efficacy would have been met if the P value for the difference between groups was <0.001 using a proportional odds model with independent covariates of group assignment (higher, intermediate, or lower SpO₂ target) and time. A stopping boundary for futility was not pre-specified. After conducting the planned interim analysis, the DSMB recommended the study continue without modification.

The DSMB reserves the right to stop the trial at any point, request additional data or interim analyses, or request modifications of the study protocol as required to protect patient safety.

Use of the conservative Haybittle-Peto boundary ($P < 0.001$) will allow the final analysis to be performed using an unchanged level of significance ($P = 0.05$).

23. Pre-specified Baseline Co-variates

We will repeat the primary analysis with adjustment for the following pre-specified baseline covariates: age (continuous), sex (male, female), race and ethnicity (Hispanic, Non-Hispanic Black, Non-Hispanic White, Other), source of ICU admission (ED, hospital ward, another ICU in the study hospital, operating room, outside hospital), vasopressor receipt (yes, no), and acute diagnoses at enrollment (cardiac arrest, acute myocardial infarction, sepsis or septic shock, acute respiratory distress syndrome), and severity of illness as assessed by the non-respiratory SOFA score.

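### Supplement 21 scores SpO₂ compliance over time when the protocol does not set the target, and the resulting misclassification depends on the arm

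*Combined protocol and SAP*

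**What the plan says.** Supplement section 21 sets the denominator: "All SpO₂ values measured during invasive mechanical ventilation are assessed for compliance with the assigned SpO₂ target". A value is compliant with the trial protocol if any of four conditions holds:

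1. "Measured SpO₂ is within the target range".
2. It is above range on FiO₂ 21%.
3. It is below range on FiO₂ 100%.
4. "Measured SpO₂ occurs after treating clinicians have completed an SpO₂ target modification sheet".

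The goal ranges are 88-92% (Lower), 92-96% (Intermediate) and 96-100% (Higher).

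The SAP (Oxygen Titration) and the 2021 protocol (section 7.1) limit when the protocol sets the target. Control runs from enrolment and ends at the earliest of extubation, transfer out of a study location, a modification sheet, or the end of the two-month period. It is also suspended outside a study location and when oxygen is given for another purpose; the example is "when an FiO₂ of 1.0 is being administered for a procedure". Supplement section 8 says of patients still ventilated when the period ends that they keep the assigned target until midnight, "after which time treating clinicians determine the SpO₂ target with which the patient is managed". It says the same of patients who return to ventilation in a later period.

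Supplement section 20 lists the separation measures, starting with "SpO₂ during invasive mechanical ventilation". They have no pass or fail rule.

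**The concern.** Compliance is meant to show whether the assigned target was delivered when the protocol asked for it. Six situations end or suspend protocol control. Section 21 deals with two: extubation, because only ventilated values are counted, and the modification sheet, through condition 4. Transfer out, time outside a study location, period end and oxygen given for another purpose have no exception. Since one kind of off-protocol time is already excused, this looks like an omission rather than a choice.

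The error need not be equal across arms, because the same SpO₂ and FiO₂ can pass in one arm and fail in another. Readers will use adherence to judge whether a null result is a true null. The plan reasons this way itself: Supplement section 3 partly discounts a 1000-patient null trial for modest separation, and protocol section 7.1 cites 95% compliance in a prior trial in the same ICU. Against that benchmark, a spurious arm difference of a few points would be noticed.

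**Working it through.** **Step 1. Apply the four conditions.** Inputs: the goal ranges and section 21, with no modification sheet. Every integer SpO₂ from 70 to 100 was scored as if the same value occurred in each arm.

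| FiO₂ | SpO₂ | Lower | Intermediate | Higher |
|---|---|---|---|---|
| between 0.21 and 1.0 | 97-100 | fail | fail | pass |
| | 96 | fail | pass | pass |
| | 93-95 | fail | pass | fail |
| | 92 | pass | pass | fail |
| | 88-91 | pass | fail | fail |
| | below 88 | fail | fail | fail |
| 1.0 | 97-100 | fail | fail | pass |
| | 93-96 | fail | pass | pass |
| | 92 or below | pass | pass | pass |
| 0.21 | 96-100 | pass | pass | pass |

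Fail/fail/pass occurs only at 97-100% on FiO₂ above 0.21. On FiO₂ 1.0 the Higher arm passes at every SpO₂, because a value is either in range or excused as below range on 100% oxygen. At lower SpO₂ on intermediate FiO₂ the advantage moves to Intermediate or Lower.

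**Step 2. How much time follows period end in the primary set?** The plan's figures are a median ventilation time of 3 days (IQR 3-5), a 7-day washout, and 98% of primary-analysis patients not crossing. Assumptions: a 61-day block, enrolment uniform over the first 54 days, and ventilation continuing in the study ICU. The remaining time r then runs from 7 to 61 days. The shape of the duration distribution is not given, so three shapes are tried.

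- *Half at 3 days or less, then a tail halving every 2 days (matches the 5-day upper quartile).* Tail mean m = 2/ln 2 = 2.885 days, and the share ventilated beyond 7 days is 0.5 × 0.25 = 0.125.
  - Share crossing ≈ m × 0.125/54 = 0.7%.
  - Post-period days per patient ≈ m² × 0.125/54 = 0.0193.
  - With mean duration 3.7 to 4.4 days (lower half spread over 0-3 days, or all at 3), post-period time is 0.4% to 0.5% of ventilated time.
- *Lognormal, median 3, upper quartile 5, capped at 28 days (simulated).* Share crossing 0.9%; post-period time 1.0%.
- *Plain exponential, median 3 (upper quartile 6, so too heavy).* m = 3/ln 2 = 4.33. Share crossing and post-period share are both m × e^(−7/4.33)/54 = 4.33 × 0.198/54 = 1.6%, or about 1.5% of time with the 28-day cap.

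All three agree with the plan's 98%. Later-period re-ventilation is not counted.

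**Step 3. Effect on measured compliance.** Let f be the off-protocol share of values, c on-protocol compliance and p the off-protocol pass rate. Measured compliance = c(1 − f) + f·p, so with equal c the difference between two arms is f times the difference in p, and at most f. The documents give neither c nor a total f. With c = 80% assumed in every arm (Lower/Intermediate/Higher):

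| f | all off-protocol values 97-100%, FiO₂ above 0.21 | all 93-95%, FiO₂ between 0.21 and 1.0 |
|---|---|---|
| 1% | 79.2/79.2/80.2 | 79.2/80.2/79.2 |
| 2% | 78.4/78.4/80.4 | 78.4/80.4/78.4 |
| 5% | 76/76/81 | 76/81/76 |

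Restricting to protocol-controlled time returns 80% in every arm.

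**Step 4. Separation.** If off-protocol SpO₂ is the same in all arms, the Lower-to-Higher contrast of 8 points (98 − 90) becomes 8(1 − f): 7.92, 7.84 and 7.6 points for f of 1%, 2% and 5%.

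**The case against.** The strongest reply is that little depends on this. No per-protocol analysis, compliance threshold or test uses the metric, and the VFD comparison and its 92% power do not change. That stands.

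A reader might infer that off-protocol time always counts against Lower and Intermediate and in favour of Higher. Step 1 does not support that. After period end clinicians choose the target, and nothing says they choose 97-100%. Supplement section 4 reports, from another trial, a median lowest SpO₂ of 94% and a median highest FiO₂ of 0.5 at 6-24 hours; that pair would pass in Intermediate and fail in both other arms.

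A reader might also find much larger post-period shares: about 40% of ventilated time for washout-week enrolees, and 5-6% across all enrolled under the median-3, upper-quartile-5 shapes. Washout enrolees are outside the primary analysis and enter only a VFD sensitivity analysis. No compliance report is planned for that set.

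Nor are the first 15 minutes off-protocol. Control starts at enrolment, and early exposure is part of the rationale for the design.

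For separation, measuring over all ventilation is defensible. An intention-to-treat result is interpreted against the contrast actually delivered, so the dilution in Step 4 is real exposure and not measurement error. Dropping transport and procedures would also discard hypoxemia episodes.

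Two practical points stand. Supplement section 6 describes SpO₂ archiving for the study ED and ICU, so values from elsewhere may not reach the dataset. Transport and procedural intervals are not among the data elements in Supplement section 18.

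None of this answers the mismatch itself: section 21 says it judges compliance with the trial protocol, yet it scores time that the protocol disclaims.

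**Conclusion.** The point holds for compliance. Section 21 misclassifies values from after period end, from outside a study location (if captured) and from oxygen given for another purpose, and the direction depends on the arm, the SpO₂ and the FiO₂. The clearest one-sided case is procedural FiO₂ 1.0, which can lower compliance in Lower and Intermediate but never in Higher.

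The size is probably small in the primary set. Post-period time is about 1% of ventilated time (0.4% to 1.6% over the shapes tried), so that component alone can shift the gap between two arms by about one point at most. The transport and procedural shares are unknown; the 2% and 5% rows are illustrations. The result assumes uniform enrolment and the plan's ventilation durations. It does not extend to the primary analysis, and it does not show the separation measures to be wrong.

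**What to change.** - In Supplement section 21, limit the compliance denominator to SpO₂ values from enrolment onward, while the patient is ventilated in a study location and within the two-month period of enrolment. Exclude procedural FiO₂ 1.0 where it is charted. Report the all-values compliance figure alongside, and name the analysis population.
- In Supplement section 20, keep the separation measures and the hypoxemia and hyperoxemia episodes over all ventilation. Add the protocol-controlled-window version as a supplement.
- Reconcile the SAP's Oxygen Titration text, under which control ends at the earliest of four events including extubation and transfer out, with Supplement section 8, under which the assigned target continues on return within the same period. Section 8 may be meant as the detail behind the SAP text, but the window needs one unambiguous statement.

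Cost: a wording change and a filter on data archived every 60 seconds. Period end is a calendar date, and location needs transfer times. The weak part is procedural oxygen: charting may be incomplete and, in an unblinded trial, could differ by arm. Some such values will remain in the window, which is a further reason to show both figures.
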